- Dental prophylaxes in the last 6 months

Sample size calculation

The primary outcome is the development of new dental caries in the children over the 24-month study period. Based on the previous oral health promotion conducted among healthy preschool children in Hong Kong (Jiang M., 2013), the mean dmfs in control group and intervention groups are 0.3 (SD = 1.3), 0.2 (SD = 0.7), 0.4 (SD = 1.2). We assumed that the mean dmfs in control group and test group are 0.7 (SD = 1.0) and 0.3 (SD = 0.5). The program G* power 3.1.9.2 is used for sample size calculation: two-tail test, a =0.05, at a power of 95%. This give

a sample size target of 105 children per group. Considering 30% overestimation to allow for dropout in 2 years, totally 300 children will be invited, with 150 children per group.

Baseline information

Baseline information will consist of the following components:

- Clinical oral examination
- Tooth-brushing performance observation
- Questionnaire-based survey

Clinical oral examinations will be performed according to the following criteria: i) Caries status were assessed by the International Caries Detection and Assessment System(ICDAS); ii) Oral hygiene status by Simplified oral hygiene index of Greene and Vermilion (OHI-S); iii) gingival health status by Modified Gingival Index of Lobene (MGI). Dental examination will be performed at Special Child Care Centers by a pediatric dentist with a disposable mouth-mirror attached to an LED light. Tell- Show-Do (TSD) technique will be used to improve children's cooperation level. Tooth-brushing performance will be assessed by two observers. There will be 13 steps listed in the assessment form, steps which are performed by child or parent will be recorded respectively, as well as the total time for each tooth-brushing session. After dental examination and tooth-brushing assessment, a standard hands-on toothbrushing training will be provided immediately to each child and his/her parent. Oral health instruction will also be illustrated to the participants, reinforced by social stories or conventional leaflets. Questionnaires regarding children's oral health related behaviours, family demographic information and parents' oral health literacy assessment will be completed by parents, while questionnaires assessing children's developmental profile will be filled by staff in Special Child Care Centers.

Allocation

3

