Concealed block randomization at school levels will be used to allocate subjects into 2 group. The randomised sequence will be generated by an investigator who do not participate in the outreach service. The allocation sequence will be sealed in an envelope, and opened at the Special Child Care Centres by an assistant, who will also be responsible for delivering the materials to children and their parents. Hence, children (participant) and investigators (outcome assessor) will not know the randomised sequence. After a standard tooth-brushing training and oral health instruction, Group 1 will be set up as a positive control, receiving standard oral-health education leaflets issued by the local government, while Group 2 will act as test group, receiving social stories developed and validated by the investigators.

Follow-up appointments

Commercially available toothbrushes and fluoridated toothpaste will be delivered to each child and renewed at every three months. Meanwhile, the old toothbrush and remaining toothpaste will be returned, and toothpaste usage and toothbrush wear will be monitored. Follow-up assessments will be performed at 6-month, 12-month, 24-month. Education materials about "healthy diets" will be emphasized at 6-month follow-up, and dental-visit related education materials will be emphasized at 12-month follow-up. Tooth-brushing training was reinforced at each follow-up appointment. Education material about tooth brushing, healthy diets and dental visit will be illustrated to children and their parents, and parents will be encouraged to read those materials to their children in their daily lives. Oral examination and tooth-brushing assessment in follow-up appointment will be performed using the same methods and criteria as baseline; all parents or primary caregivers will complete a set of questionnaires on their attitudes towards the interventions and their children's oral-health related behaviours.

Significance

The present study will provide scientific evidence of effective oral health care for children with special needs. Meanwhile, the interventions adopted in the control group and test group have potential benefits to encourage the children with special needs to take care of themselves by learning tooth brushing independently at an early age status, supporting their relatively independent life in the future.

References

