Statistical Analysis Plan

Official Title:

Effectiveness of visual pedagogy-assisted tooth-brushing training among preschoolers with special needs for oral health promotion

Date: 2015.11.22

All the data will be analysed using IBM SPSS. Variables from the questionnaires will be analysed by t test for independent samples or its non-parametric equivalent for continuous data and Chi-square tests for categorical data. Descriptive statistics of cooperation with tooth brushing in each group will be determined and variations in cooperation with tooth-brushing and developmental level of special needs will be determined by Chi-square statistics. McNemar's test will be used to analyse whether children's oral-health related behaviours will be changed before and after intervention. Then regression analyses will be conducted to determine developmental factors associated with children's oral health status or cooperation in conducting tooth brushing, accounting for child's age and gender in the model. Variations in simplified oral hygiene index, modified gingival index, caries incidence, number of completed tooth brushing tasks and time taken to complete the overall task will be determined using repeated measures ANOVA (or Friedmann ANOVA for nonparametric data). Inter-group comparisons of the above outcome variables with respect to baseline will be determined using paired t-test (or Wilcoxon signed rank for nonparametric data). Intra-group comparisons of at baseline, 6-month, 12-month, and 24-month will be conducted using student's t-test (or Mann Whitney U test for nonparametric data). Magnitude of change will be derived through effect size calculation (mean change/ SD of baseline values) to provide an indication of clinical significance of the results. The significance levels will be set to be $P < 0.05$.

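### The SAP's rank fallback for the longitudinal analysis, Friedman's test, cannot compare arms, and the one rank test that can appears under the intra-group label

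*SAP*

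**What the plan says.** The SAP is one paragraph, and three consecutive sentences in it matter here.

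- Longitudinal analysis. The outcomes are listed as "Variations in simplified oral hygiene index, modified gingival index, caries incidence, number of completed tooth brushing tasks" and time for the whole task. The method is repeated measures ANOVA, "or Friedmann ANOVA for nonparametric data". No arm factor or arm-by-visit term is named for either test.
- Comparisons called inter-group, made with respect to baseline. These "will be determined using paired t-test (or Wilcoxon signed rank for nonparametric data").
- Comparisons called intra-group, at baseline, 6, 12 and 24 months. These "will be conducted using student's t-test (or Mann Whitney U test for nonparametric data").

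The SAP does not say when an outcome counts as nonparametric.

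In the protocol, Sample size calculation states: "The primary outcome is the development of new dental caries in the children over the 24-month study period". It then gives the planning values: "We assumed that the mean dmfs in control group and test group are 0.7 (SD = 1.0) and 0.3 (SD = 0.5"). Under Allocation, randomization is in blocks at school level to leaflets or social stories. Both arms receive the same hands-on training, brushes and fluoride toothpaste, and under Follow-up appointments: "Tooth-brushing training was reinforced at each follow-up appointment".

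**The concern.** Repeated measures ANOVA and Friedman's test are offered as interchangeable, but they are counterparts only when the question is change over visits in a single group. Repeated measures ANOVA can be extended to ask whether two arms change differently. Friedman cannot. Pooled over all children it ignores arm, and run in each arm it gives two separate tests of time and no contrast between them.

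An analyst who follows the text for a skewed outcome therefore gets Friedman for the longitudinal question and Wilcoxon signed rank for the comparison labelled inter-group. Both are within-child tests. No rank test in the SAP is both labelled as comparing arms and able to do so.

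The design makes this matter. The arms share most of the intervention, so movement over time is expected in both, and cumulative caries can only rise. A significant Friedman result is then close to guaranteed for caries and could be reported as if it bore on the trial's question.

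**Working it through.** **1. What the sample size assumes.** Inputs from Sample size calculation: means 0.7 and 0.3, SDs 1.0 and 0.5, two-sided alpha 0.05, power 95%.

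- Pooled SD = √((1.0² + 0.5²)/2) = √0.625 = 0.791; d = 0.4/0.791 = 0.506.
- Normal approximation: n = 2 × (1.960 + 1.645)² × 0.625/0.16 ≈ 101.5, so 102 per group.
- Noncentral t: 103 at d = 0.506, and exactly 105 at d rounded to 0.5.
- Dropout: 105/(1 − 0.30) = 150 per group.

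The stated 105 and 150 are reproduced. The trial was sized for a comparison of two independent groups, which Friedman does not make.

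**2. Is the rank branch likely for caries?** Caries counts cannot be negative. A normal model puts Φ(−mean/SD) of children below zero.

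| Figures in the protocol | Mean/SD | Share below zero |
|---|---|---|
| Planned control 0.7 (1.0) | 0.70 | 24% |
| Planned test 0.3 (0.5) | 0.60 | 27% |
| Source study 0.3 (1.3) | 0.23 | 41% |
| Source study 0.2 (0.7) | 0.29 | 39% |
| Source study 0.4 (1.2) | 0.33 | 37% |

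The SD exceeds the mean in all five rows. The rank branch is likely, but this is an inference.

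**3. What Friedman's statistic contains.** For n children and k visits, before tie correction, it is 12/(nk(k+1)) × ΣRⱼ² − 3n(k+1), where Rⱼ is the sum over children of the within-child rank of visit j. Arm does not appear. In one simulated dataset, shuffling the arm labels left the statistic at 146.29 (p about 2 × 10⁻³¹), while the Mann-Whitney p-value at 24 months moved from 0.018 to 0.148.

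**4. Cumulative new caries.** The assumptions are 105 per arm, zero at baseline, new caries split 25/25/50% over the three intervals, children independent, and 1,000 trials per scenario. Counts with mean 0.7 are negative binomial with SD 1.0. Counts with mean 0.3 are Poisson, with SD 0.55, slightly above the stated 0.5.

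| Control/test mean | Friedman pooled | Friedman in each arm | Mann-Whitney at 24 months |
|---|---|---|---|
| 0.7/0.3 | 100% | 100% and 100% | 90% |
| 0.7/0.7 | 100% | 100% and 100% | 6% |
| 0.3/0.3 | 100% | 100% and 100% | 6% |

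**5. Outcomes that can move either way.** Assumptions: 105 per arm, four visits, correlation 0.5 unless stated. The documents give no correlation.

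- Both arms improve by 0.3 SD with no arm difference: pooled Friedman is significant in 92–99% of trials, depending on the shape of change over visits; Mann-Whitney on 24-month change in 4–6%.
- Arms differ by 0.6 SD: pooled Friedman is significant in about 5% if the arms move by exactly opposite amounts, but in 91–100% with improvements of 0.6/0, 0.75/0.15 or 0.9/0.3 SD.
- Equal true improvement, Friedman run per arm: exactly one arm is significant in 31–48% at 0.15–0.30 SD, 0–5% at 0.5 SD, and 1–6% at 0.3 SD with correlation 0.8. The overall range is about 0–50%. For caries it is 0%, because both arms are always significant.

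**The case against.** The strongest reply is that the SAP never assigns Friedman to the arm comparison. Its sentence speaks of variation in the outcomes and names no arm term for repeated measures ANOVA either. Read as change over visits, Friedman is the usual rank counterpart. A usable rank test of arms is also present: Mann-Whitney is an independent-samples test, and the SAP lists it at every visit. For new caries counted from zero, Mann-Whitney at 24 months is the same test as Mann-Whitney on 24-month change.

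Much of this stands. A reader might infer that the SAP contains no way to compare arms for skewed data. The documents do not support that, because the test is there under a label that looks swapped with its neighbour's. A reader might also infer that the SAP directs caries to Friedman. It does not say so: there is no switching rule, and the trial was sized on means using these same figures. Finally, a reader might infer that Friedman will miss a true arm difference. That needs the two arms' trends to cancel, which sits badly with a design in which both arms receive the same training. With other splits of the same difference Friedman is usually significant, though this is still no evidence about arm.

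What the reply does not remove is that the text, as labelled, directs the inter-group rank comparison to a within-child test and leaves the longitudinal analysis with no stated arm term in either branch.

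**Conclusion.** The concern holds in this limited form. Friedman tests time only, whatever the data, because its statistic contains no arm label; that needs no simulation. The SAP names no arm or arm-by-visit term for the parametric branch, and its inter-group and intra-group labels appear swapped and need correcting.

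For cumulative new caries, Friedman was significant in 100% of simulated trials with or without an arm effect. That figure assumes caries incidence is accumulated from zero at baseline and uses the count distributions above. The significant-in-one-arm-only pattern is a risk of about 0–50% for the other outcomes, depending on assumed effect and correlation, and does not apply to caries.

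The plan should be changed, since the ambiguity reaches the primary outcome, but this is a matter of specification and labelling. The sample size is unaffected by this point.

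**What to change.** In the SAP:

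1. Correct the labels, so that paired t and Wilcoxon signed rank are intra-group and independent-samples t and Mann-Whitney are inter-group.
2. State that Friedman and Wilcoxon signed rank describe change within an arm only and are not evidence of an arm effect.
3. Name the arm comparison: a longitudinal model with arm, visit and arm-by-visit, reporting the 24-month arm contrast with a 95% CI. For new caries, an example is a log-link count model with robust standard errors, fitted to the follow-up visits because the baseline value is zero by definition. It should take account of the school-level randomization described under Allocation.
4. If a rank test is preferred, apply Mann-Whitney to 24-month new caries, and to each child's 24-month change for outcomes with a baseline value. Say how school is handled there too.
5. Fix in advance which method each outcome receives.

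The cost is SAP wording, slightly more analysis work and an added model assumption. SPSS, the software named in the SAP, offers generalized estimating equations and generalized mixed models. Choosing Mann-Whitney for caries avoids the model assumption, but in the simulation above it reached 90% power, against the 95% planned for a comparison of means.

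### The SAP gives paired tests to between-group comparisons and independent-sample tests to within-group comparisons, so no valid between-arm test of the primary caries outcome is stated

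*SAP*

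**What the plan says.** The protocol (Sample size calculation) defines the primary endpoint: "The primary outcome is the development of new dental caries in the children over the 24-month study period". The Trial design and Allocation sections describe two parallel groups, leaflets and social stories, and mention no matching of children.

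The SAP lists five outcomes, caries incidence among them, and gives three rules for them:

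- For variation in these outcomes, the rule is that it "will be determined using repeated measures ANOVA (or Friedmann ANOVA for nonparametric data"; no group factor is named there.
- For comparisons labelled as between groups, the rule reads: "Inter-group comparisons of the above outcome variables with respect to baseline will be determined using paired t-test". Wilcoxon signed-rank is the nonparametric alternative.
- For comparisons labelled as within groups, the rule reads: "Intra-group comparisons of at baseline, 6-month, 12-month, and 24-month will be conducted using student's t-test". Mann-Whitney U is the nonparametric alternative.

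The SAP's only explicit independent-samples t-test is for questionnaire variables. McNemar's test is for behaviour before and after the intervention. The regression looks for developmental factors, adjusts for age and gender, and does not mention treatment arm.

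**The concern.** A paired test needs two measurements on the same child or on matched children. The arms contain different, unmatched children, so it cannot compare them. Conversely, Student's t and Mann-Whitney assume independent samples, which repeat visits of the same children are not. Both the parametric and the nonparametric tests sit under the wrong label, which points to the words for between-group and within-group having been exchanged.

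The effectiveness conclusion is at stake. Run against baseline, the paired test asks only whether caries accumulated within an arm. Both arms can show a significant change with no difference between them. An analyst who notices the swap must still settle the primary test, and the visit at which it applies, without a written rule.

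**Working it through.** **Inputs from the protocol (Sample size calculation).** "We assumed that the mean dmfs in control group and test group are 0.7 (SD = 1.0) and 0.3 (SD = 0.5"); "two-tail test, a =0.05, at a power of 95"%; "a sample size target of 105 children per group"; then "Considering 30% overestimation to allow for dropout in 2 years, totally 300 children will be invited, with 150 children per group".

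**1. Which test the trial was sized for.**
- Root-mean-square SD = √((1.0² + 0.5²)/2) = 0.791, so d = 0.4/0.791 = 0.506.
- Independent two-sample t, two-sided 0.05, power 95%: 103 per group at d = 0.506. With d rounded to 0.5 it is exactly 105 (power 0.9501).
- Dropout: 105/(1 − 0.30) = 150 per group, as planned.
- For contrast, a paired t-test needs 53 pairs if its standardised effect is also taken as 0.506. That equality is an assumption.

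The planned figure is therefore that of an independent between-arm comparison.

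**2. What the paired test answers.** Assume that the stated means are 24-month increments and that 105 children per arm are evaluable; √105 = 10.25.
- Control, paired: t = (0.7/1.0) × 10.25 = 7.17.
- Test group, paired: t = (0.3/0.5) × 10.25 = 6.15.
- Between arms, independent: t = 0.4/√(1.0/105 + 0.25/105) = 3.67.

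The first two test each arm's mean increment against zero. Only the third compares treatments.

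**3. No treatment effect.** Negative-binomial increments with mean 0.7 and SD 1.0 were simulated in both arms, 20,000 trials. The paired test was significant in both arms in 100% of trials; the independent between-arm test was significant in 4.8%.

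**4. Independent tests on repeat visits.** The independent t-test uses a standard error proportional to √2, but the true one is proportional to √(2(1 − r)), where r is the correlation between visits. The documents give no r and no within-arm change, so r = 0 to 0.7 and a change of 0.3 SD are assumptions (n = 105, 100,000 replicates).

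| r | False positives, independent t | Power, independent t | Power, paired t |
|---|---|---|---|
| 0 | 5.0% | 58% | 58% |
| 0.5 | 0.54% | 61% | 86% |
| 0.7 | 0.04% | 64% | 98% |

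The paired test keeps its 5% level throughout.

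**5. Whether another SAP method fills the gap.** The independent t-test is confined to questionnaire items, McNemar's test is before-and-after, and the regression has no stated arm term. Repeated measures ANOVA could carry arm as a between-child factor, but no group or group-by-time term is given. Its Friedman fallback has no between-group factor. Caries counts with an SD above the mean are skewed, so the fallback may well be invoked.

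**The case against.** The strongest reply is that this is a visible slip. The reference to baseline belongs with a paired test, the list of visits fits arm-by-arm comparison, and exchanging the labels makes both sentences conventional. A paired test between unmatched arms cannot sensibly be run, so the error should be caught, and both correct tests are already in the plan. This stands as an explanation of how the error arose. It does not supply a primary analysis: after the exchange there are still several visits, a t or rank test, and an ANOVA with no stated term to choose from.

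On magnitude, the 100% figure is not a false-positive rate. Each paired test correctly rejects a hypothesis of no caries accumulation. It misleads only if significance within an arm is taken as evidence of a treatment effect, and no sentence in the plan says to do so. That is fair; the figure shows only that the paired tests carry no information about the difference between arms. The power losses in step 4 concern within-arm change, rest on assumed correlations, and are secondary.

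The ANOVA also deserves credit: on the parametric route the fault is an unstated term rather than an unsuitable method.

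Finally, the Allocation section speaks of block randomisation at school level. If schools were the randomised unit, a simple independent test would need adjustment. That is a separate matter and does not rescue the current wording.

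**Conclusion.** The concern holds. As written, the SAP assigns an unusable test to the between-arm comparison of the primary outcome, and no other sentence states a valid one. This rests on the text alone, with no numerical assumption. That the labels were transposed is probable, not certain.

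The sizes in steps 2 and 3 depend on reading the assumed mean dmfs values as 24-month increments with 105 evaluable children per arm; those in step 4 depend on the assumed change and correlations. It is an error of specification, not of sample size, since both 105 and 150 reproduce. Because it affects the primary outcome, it should be corrected before analysis.

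**What to change.** Exchange the two rules in the SAP:

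- **Between groups:** independent two-sample t or Mann-Whitney test, with the 24-month caries increment named as the primary comparison on which the effectiveness conclusion rests.
- **Within groups, change from baseline:** paired t or Wilcoxon signed-rank, labelled descriptive.
- **Repeated measures ANOVA:** if kept for comparing groups, state the group-by-time term, and do not rely on Friedman for that purpose.

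The cost is SAP wording. The sample size does not change, because 105 per group already corresponds to the independent test with the child as the unit of analysis.

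### The SAP compares the arms on OHI-S, MGI, brushing steps and brushing time without adjusting for the baseline values the trial already collects, which costs precision but not validity

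*SAP*

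**What the plan says.** Under Baseline information, the Protocol lists OHI-S, MGI and a 13-step brushing assessment in which "steps which are performed by child or parent will be recorded respectively, as well as the total time for each tooth-brushing session". Under Follow-up appointments, the same examination and brushing assessment are repeated by the same methods at 6, 12 and 24 months.

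The SAP, which is a single section, applies the following to these outcomes:

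- Repeated measures ANOVA, or Friedman: "Variations in simplified oral hygiene index, modified gingival index, caries incidence, number of completed tooth brushing tasks and time taken". No arm term is stated, and Friedman has none.
- Paired t or Wilcoxon signed rank: "Inter-group comparisons of the above outcome variables with respect to baseline will be determined using paired t-test". These tests compare a child with itself.
- Student's t or Mann-Whitney U at each visit: "Intra-group comparisons of at baseline, 6-month, 12-month, and 24-month will be conducted using". These are two-sample tests, although the sentence calls them intra-group.
- A descriptive magnitude of change: "effect size calculation (mean change/ SD of baseline values".

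The only adjusted model has another purpose: "Then regression analyses will be conducted to determine developmental factors associated with" oral health status or cooperation, with age and gender as the covariates.

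**The concern.** Baseline enters the SAP as a repeated level, as a paired reference, as a visit to be tested and as a standardising SD. It is never a covariate in a comparison of the arms. A value that predicts the follow-up measurement is therefore collected on every child and then left out of the one place where it would sharpen the treatment estimate.

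At stake is the width of the intervals for four outcomes that the intervention targets directly. There is also a problem of identification. The tests called inter-group cannot compare groups, and the tests called intra-group can, so a reader cannot be sure which test is the arm comparison. The labels may be swapped, which leaves a follow-up-only comparison at each visit. Or the test names may be swapped, which would make the comparison relative to baseline a two-sample test of change. Neither repair introduces baseline adjustment. The point does not concern caries, which is the primary outcome.

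**Working it through.** **The plan's own figure.** The Protocol's Sample size calculation gives "a sample size target of 105 children per group" for caries, from means of 0.7 (SD 1.0) and 0.3 (SD 0.5), two-sided 0.05 and 95% power. The pooled SD is √((1.0² + 0.5²)/2) = 0.791, so d = 0.4/0.791 = 0.506. The normal formula gives 102 per group and noncentral t gives 103; with d rounded to 0.5, noncentral t gives exactly 105. "Considering 30% overestimation to allow for dropout in 2 years" gives 105/0.7 = 150. The figure reproduces, and this point does not make it wrong. I use 105 below only as the expected number of completers per arm.

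**Precision for the four outcomes.** The inputs are 105 per arm (Protocol), outcome SD set to 1 at every visit, independent children, and r assumed at 0.1, 0.3, 0.5 and 0.7. The formulas for the SE of the arm difference are:

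- follow-up only: √(2/105) = 0.138
- change score: √(4(1 − r)/105)
- ANCOVA: √(2(1 − r²)/105)

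The ANCOVA variance is therefore 1 − r² of follow-up only, and (1 + r)/2 of the change score.

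| r | ANCOVA variance / follow-up only | ANCOVA variance / change | SE ANCOVA | SE follow-up only | SE change |
|---|---|---|---|---|---|
| 0.1 | 0.99 | 0.55 | 0.137 | 0.138 | 0.185 |
| 0.3 | 0.91 | 0.65 | 0.132 | 0.138 | 0.163 |
| 0.5 | 0.75 | 0.75 | 0.120 | 0.138 | 0.138 |
| 0.7 | 0.51 | 0.85 | 0.099 | 0.138 | 0.107 |

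Multiplied by 1.96, the 95% half-width is 0.271 SD for follow-up only, against 0.269, 0.258, 0.234 and 0.193 for ANCOVA.

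**The repeated measures ANOVA.** If an arm-by-time term was intended, baseline is one of its outcome levels. The contrast of a follow-up visit with baseline is then the change-score column. Below r = 0.5 that is less precise than ignoring baseline altogether.

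**Non-normal outcomes.** I simulated 4,000 trials per cell with 105 per arm, lognormal brushing time (log SD 0.8), a 0–13 step count and an assumed latent shift of 0.4 SD. The r values were 0.3, 0.5 and 0.7. Mann-Whitney had 79–81% power, and rank ANCOVA had 84%, 89% and 97–98%. ANCOVA on untransformed time had 72%, 77% and 89%, below Mann-Whitney at r of 0.3 and 0.5. At r = 0.1, rank ANCOVA and Mann-Whitney both had 79% on skewed time.

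**Dropout.** I simulated no true effect, with dropout linked to the outcome in one arm only and 150 per arm falling to 105. Where dropout depended on the last observed value, the bias was 0.05–0.20 SD for the 24-month two-sample test, 0.03–0.06 for ANCOVA and 0.01–0.05 for a completer change score. Where it depended on the unseen value, the biases were 0.11–0.25, 0.06–0.17 and 0.03–0.11. ANCOVA was more biased than completer change in 11 of 12 cells.

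**The case against.** The strongest reply is that nothing here is an error. Two-sample tests by visit are legitimate, the outcomes are not primary, and the SAP's references to baseline and to mean change suggest that its authors meant to use baseline through an arm-by-time ANOVA or change scores. On that reading the gain at r = 0.7 is about 8% in SE (√0.85 = 0.922), not the 29% that follow-up only suggests (√0.51 = 0.714). The interval is 24 months, in children aged 2 to 6 who are trained in both arms, so r could also be low. At 0.1 the gain over follow-up only is about 0.5%. All of this stands and limits the size of the point. It does not remove it, because on a suitable scale ANCOVA is at least as precise as either reading at every r shown.

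A reader might infer three stronger things that the documents do not support:

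- *That the planned tests are invalid or biased.* Allocation is randomised, so with the analysis at the right unit they are not.
- *That chance baseline imbalance is a further harm.* A baseline difference of 0.2 SD or more has about a 15% chance per outcome, and at r = 0.5 it would move the follow-up-only result by 0.10 SD. But that movement is part of the variance already counted: 2/105 = 2(1 − r²)/105 + 2r²/105, and the last term is what ANCOVA removes.
- *That adjustment would solve the dropout problem.* The simulation above shows that it would not.

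**Conclusion.** The point holds as a modest, inexpensive improvement. For OHI-S, MGI, completed steps and brushing time, the SAP contains no baseline-adjusted arm comparison, and its labels obscure which test compares the arms. The consequence is lost precision on non-primary outcomes. Against follow-up only, ANCOVA would cut the variance by 1%, 9%, 25% or 49% at r of 0.1, 0.3, 0.5 or 0.7. Against a change score it would cut it by 45%, 35%, 25% or 15%.

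These sizes rest on an assumed r, equal SDs across visits, a suitable scale and independent children. The Protocol's Allocation section describes block randomisation at school level. If that means whole schools are allocated, the standard errors above do not apply. They would grow by √(1 + (m − 1)ICC), for example from 1.02 (m = 5 children per school, ICC 0.01) to 1.70 (m = 20, ICC 0.10), where m and ICC are both assumed. The randomised unit and the sensitivity to missing data are separate points. The labels need correcting whatever r is.

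**What to change.** For these four outcomes, make the arm comparison at each planned follow-up visit (6, 12 and 24 months) an ANCOVA of the follow-up value on arm and baseline value. Report the adjusted difference with its 95% CI. The SAP already tests each of these visits, so this adds no comparisons.

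Where the SAP would fall back on Mann-Whitney, use a log scale and report a ratio with its CI, or use rank ANCOVA for the test only, since ranks give no difference in original units. Do not default to untransformed ANCOVA on skewed brushing time.

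Correct the inter-group and intra-group labels so that the arm comparison can be identified, and state whether the repeated measures ANOVA has an arm term.

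The cost is SAP wording and modest extra work in SPSS, with no new data and no change in sample size. The downside is reliance on the scale and model assumptions, and ANCOVA gives no protection against dropout that depends on the outcome.
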